The randomized repeated-measures design addresses threats to both internal and external validity and is strengthened by multiple replications (Shaddish, Cook, & Campbell, 2002). Caregivers will report treatments (i.e. medications) added during the 3 months to identify any potential influences. The Data Safety Monitoring panel will discuss new treatment developments and their impacts annually. Supervised training and monitoring protocols will assure fidelity. Measurement fidelity will be maintained by using measures with established reliability and validity and by research team training and monitoring. Research assistants (RAs) who code data will be blind to group assignment and video collection time to avoid expectation bias (Polit & Beck, 2007).

Aim 2. An exploratory descriptive design will identify PWD behaviors and precipitants captured in video that each caregiver identifies as their top priority. Content analysis and behavioral coding of videos will identify common behaviors (within the NDDCB framework), links to precipitants, and effective recommendations as a basis for a typology of caregiver interventions for in-home use (Dawson, et al., 1990). Actual caregiver use of interventions will be coded and audio recordings of team conferences will be transcribed and coded. Content analysis of this data will add information about characteristics predicting caregiver use of recommendations.

Aim 3. Caregiver satisfaction with effectiveness and ease of use will be evaluated and select caregivers will be interviewed and observed using FamTechCare. Video review team experts will rate the likelihood of diffusion into practice with a modified Duke Diffusion of Innovation in Long Term Care Battery (McConnell et al., 2010). Costs will be tabulated using traditional methods and compared to outcomes (PWD disruptive behavior and caregiver burden and NH placement intention), using traditional and Data-Envelopment Cost Analyses (DEA).

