Recording. Behavior Capture (see appendix E) was developed by Behavior Imaging with NIH SBIR support for monitoring children with autism. **Behavior Capture** uses a "go-back-in time" buffering technology to record when triggered, also capturing video up to 15 to 30 minutes prior to the trigger (we will use a 10 minute "go back" as was effective in our feasibility study). Including antecedents enables effective behavior assessment. **Behavior Connect** provides automatic Internet transfer of video recordings to HIPAA-secure storage.

Feasibility of using this new technology for the FamTechCare intervention was established with 5 caregiver-PWD dyads in our CTSA feasibility study (Williams et al., 2012). We will use and adapt as needed the IRB-approved protocols and procedures, protocols for encrypted HMU units and software configuration using Site Kiosk (a program that limits computer use to research-specific programs), contracts to assure HIPAA protections of video data, and training materials developed by our CTSA study team. Computers will be configured to run the high definition, wide-angle webcam and remote control with preset settings, eliminating the need for caregivers to login with names and password (avoiding added burden). HMU computers run

continuously, ready for caregivers to record when they want feedback by simply pressing a button on the remote control (that fits in a pocket or is worn around the neck). A 5-foot webcam extension cord extends the recording area and the laptop itself is portable and easy for caregivers to move. Although no password is required for the caregivers to start recording, each HMU will connect to a separate account for discreet storage requiring a logon password to limit access and protect confidentiality of the data.

Both groups will record behaviors during daily care for 3 months using a HMU. FamTechCare group videos will be immediately uploaded via the Internet to a HIPAA-secure site for expert team review and feedback in behavior management. The time and attention equivalent control group will receive only a weekly phone call from a nurse, but recorded videos will be held for review and feedback at 3 months. This encourages participation (all participants will benefit from expert video review and feedback during their study involvement).

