D5. Procedures. Each site will identify potential participants and obtain consent. As soon as 4 participants are enrolled at each site, 2 will be randomly assigned to FamTechCare and the other 2 to the Control group. This is repeated until 11 cohorts are completed. A trained research assistant (RA) will make a home visit to collect demographic data and to complete FAST staging (Sclan & Reisberg, 1992) to confirm that the PWD has moderate stage dementia. Each caregiver will complete the Revised Memory and Problem Behavior Checklist (RMPBC) to verify the presence of disruptive behaviors. The RA will assist caregivers in identifying their 3 most problematic disruptive behaviors/care situations (see D7a) as the focus for recordings and interventions and the HMU will be set up in the area where the most disturbing disruptive behaviors usually occur (as the focus for the first week). The RA will train caregivers in HMU use and provide reference books. Visits will continue until caregivers demonstrate proficiency in recording and moving the HMU using a competency checklist. If the needed, the RA will make a home visit to assist the caregiver in moving the HMU in subsequent weeks.

Caregivers will be asked to record at least one video of their identified priority disruptive behavior/care activity each day. The telehealth nurse will monitor submitted videos and prompt caregivers with reminders if needed.

Caregivers will repeat recordings of each priority disruptive behavior/care activity after using FamTechCare interventions and at 1 and 3 months. Home visits to repeat data collection will be made at 1 and 3 months in both groups.

D6. Descriptive Data. Information about caregivers and PWD that may influence study outcomes will be collected and included as covariate factors (Unruh & Wan, 2004; Yu, Evans, & Sullivan-Marax, 2005; Zimmerman et al., 2005). PWD data will include gender and dementia etiology. Data on caregiver age, competency, relationship to the PWD, and research site will also be collected for covariate analysis.

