D7. Measures. The RA will administer survey assessments to caregivers at home. Measures take less than 1 hour total to complete, limiting participant burden. Research assistants (RAs) will be trained to administer the assessments with practice and feedback sessions supervised by the PI at each site. A written protocol and a key component checklist will assure fidelity for data collection. As in our past research, 10% of assessment sessions will be audio recorded and content analyzed to establish compliance with data collection protocols.

Measures addressing study aims and hypotheses are outlined in Table 1 and detailed in the text. All measures are reliable and valid for use in dementia care research. Our established content analysis and behavioral coding protocols adapted from our prior research (Herman & Williams, 2009; Williams et al., 2011; Williams et al., 2009; Williams et al., 2005) will be used for data analyses.

TABLE 1. Specific Aims, Outcomes, and Measures

SPECIFIC AIM	Outcome	Measure (number of items and estimated time) & Analysis Plan
1. Determine effects of FamTechCare on PWD & CAREGIVER outcomes at 1 and 3 months.	PWD Disruptive behavior Stress Medication use CAREGIVER Burden Stress Depression Sleep disturbance Medication use Confidence	Compare between-group changes at 1- and 3-month: Proportions of behaviorally coded disruptive behavior in videos Revised Memory Problem Behavior Scores (31 items/15 min.) EDA data (Ashametrics) Elective psychoactive medication use (5 minutes). Compare between-group changes in 1- and 3-month scores on: Modified Zarit Burden Scale (12-items/5 min.) EDA data (Ashametrics) CES-D Scale (15 items/5min.) Pittsburg Sleep Quality Index (9 items/5 minutes) Caregiver reported psychoactive medication use (5 minutes) 3 confidence questions (see D7a) (10 min.)
2. Identify precursors of disruptive behaviors and develop a typology of interventions for caregiver in-home use.	Describe behaviors and precipitants Identify interventions and Evaluate effects	Content analysis and behavior coding of caregiver submitted videos and recorded video review team meetings. Content analysis of written intervention care plans. Behavioral coding and comparison of proportions of disruptive behavior in pre- and post-intervention videos.

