Behaviorally Coding of Disruptive Behaviors will be completed using our behavioral coding protocols from our NIH-funded R03 and R01 studies (Herman & Williams, 2009; Williams et al., 2009). We will use the Noldus Observer Video Pro (2003) software program to code disruptive behaviors, based on the operational definitions in the Resistiveness to Care scale (Mahoney et al., 1991). A computer key corresponding to each behavior state (disruptive or cooperative) is depressed when behaviors occur in the real time video recordings. Duration of each behavior state (disruptive or cooperative) is tabulated by the length of time keys remain depressed (until the key corresponding to the alternate, mutually exclusive behavior state is pressed). RAs will be trained using our protocol operational definitions for disruptive behaviors on practice materials until inter-coder agreement reaches 90% or greater. As in our prior studies, we will assess inter-coder agreement on 10% of actual study data. Retraining of coders will be provided if reliability falls below targets. RAs coding video will be blind to group and time of collection. Three recordings of videos of each priority care activity submitted at baseline, 1, and 3 months will be analyzed. The proportion of time disruptive behaviors occur will be compared within individuals and changes in the proportion of disruptive behavior compared between groups.

Caregiver-report Disruptive Behaviors. The 31-item Revised Memory and Problem Behavior Checklist (RMPB). (Roth et al., 2003; L. Teri et al., 1992) elicits caregiver reports of the behavior frequency related to 24 memory, depression, and disruptive behaviors in the past week, with Cronbach's alpha of .785.

PWD Stress. We hypothesize that FamTechCare interventions will reduce disruptive behaviors as well as stress in PWD.

PWD Medication Use. Counts of caregiver reported elective (prn) use of anxiolytics, hypnotics, and antipsychotic drugs taken by PWD in the past week will be compared between groups at 1 and 3 months.

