D7b. SPECIFIC AIM 2: Identify precursors of disruptive behaviors and develop a typology of interventions for caregiver in-home use. Recordings of team video review meetings will be transcribed and coded using qualitative content analysis to determine the most commonly occurring behaviors, precipitants, and recommended interventions within the NDDCB model framework. Interventions for each caregiver's three priority disruptive behaviors will be analyzed for effectiveness using our behavioral coding techniques (Williams et al., 2009). Patterns of disruptive behaviors in relation to antecedents and the caregiving context (i.e. lack of attention, interruption, overstimulation) will be coded using Noldus computer software based on Delgado's functional analysis system (2006). RAs (blinded to group and time of data collection) will code recordings for caregiver intervention use and disruptive target behaviors in PWD. Baseline and post-intervention data will be compared to determine the most utilized and effective interventions. Descriptive information (D6) about the dyad will be examined in relation to use of recommended interventions.

D7c. SPECIFIC AIM 3. Evaluate ease of use, satisfaction, and cost effectiveness of FamTechCare using traditional cost methods and Data Envelopment Cost-efficiency Analysis.

Ease of Use and Satisfaction. The Caregiver Satisfaction with Home Monitoring Survey (see appendix A) is a 12-item Likert checklist scale that ascertains ease of use and perceived satisfaction with the intervention. It will be completed at the end of the caregiver's study involvement. Descriptive results will be reported. In addition, our human factor expert will interview and observe five caregivers regarding FamTechCare HMU use.

Assessment of Diffusion of Innovation. The Duke Diffusion of Innovation in Long-Term Care Battery (Cain & Mittman, 2002; Kovach et al., 2008; McConnell et al., 2012; 2010) was adapted to assess critical factors determining likelihood of dissemination of the FamTechCare intervention into practice (see appendix B). The scale assesses perceptions of complexity, ease of use, compatibility with work practices, and observation. The dementia expert video reviewers will complete this questionnaire at the end of the study.

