The fixed effects in the model will include group (FamTechCare or control), site (UIHC or KU ADC), data collection time (baseline, 1, or 3 months), and all two-factor and three-factor interactions, including treatment by time interaction. A significant treatment by time interaction effect will indicate differences between the two groups. The analysis will be adjusted for important covariates, identified with baseline comparisons. With 70

subjects, 7 covariate factors meet statistical requirements for 5 to 10 subjects per covariate (Tabachnik & Fidell, 2001).

Fit of the models will be assessed using appropriate fit statistics, including Akaike information criterion (AIC) and likelihood ratio tests. To test for specific comparisons of interest, i.e. comparing treatment and control groups in terms of their mean change in PWD's disruptive behaviors, stress, and psychoactive medication use and caregivers' stress, burden, depression, sleep, and confidence (e.g., from baseline to month 3), tests of mean contrasts will be performed using parameter estimates from the fitted mixed models. Significant differences between the two groups, if they are in the expected direction, will support the hypothesis. An additional model per protocol will test changes in outcomes using only dyads in which the caregiver used recommended interventions in subsequent video recorded interactions.

D9b. Specific Aim 2. Identify precursors of disruptive behaviors and develop a typology of interventions for caregiver in-home use. We will use content analysis of caregiver submitted videos and recorded team video review meetings to tabulate the most common symptoms and behaviors. Qualitative content analysis of recorded team meetings for video review and written intervention plans for caregivers will identify key symptoms and behaviors. We will also code behaviors and symptoms exhibited by PWD in pre- and post-intervention videos submitted by caregivers. Counts will be analyzed descriptively to identify the most common symptoms and behaviors and the recommended interventions and their effectiveness.

D9c. Specific Aim 3. Evaluate ease of use, satisfaction, and cost effectiveness of FamTechCare using traditional cost methods and Data Envelopment Cost-efficiency Analysis (DEA).

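### Aim 2 would call interventions effective on before-after change in each caregiver's most problematic behaviours, with no control contrast stated

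*Combined protocol and SAP*

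**What the plan says.** The overview of Aim 2 in the Approach section sets a modest frame: "An exploratory descriptive design will identify PWD behaviors and precipitants captured in video that each caregiver identifies as their top priority". The same paragraph, however, makes the identification of effective recommendations part of the basis for a typology for home use.

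Three places describe how effectiveness will be judged:

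- D7b: "Baseline and post-intervention data will be compared to determine the most utilized and effective interventions".
- Table 1, Aim 2 row: "Behavioral coding and comparison of proportions of disruptive behavior in pre- and post-intervention videos". The Aim 1 row of the same table asks for between-group changes; the Aim 2 row does not.
- D9b: "Counts will be analyzed descriptively to identify the most common symptoms and behaviors and the recommended interventions and their effectiveness".

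Targets are set at the initial home visit (D5): "The RA will assist caregivers in identifying their 3 most problematic disruptive behaviors/care situations".

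The control arm supplies comparable material. D4 says "Both groups will record behaviors during daily care for 3 months using a HMU". D7a says "Three recordings of videos of each priority care activity submitted at baseline, 1, and 3 months will be analyzed", and changes are then compared between groups for Aim 1. In D7b the Aim 2 coders are blind to group, which implies that control clips are among those coded.

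**The concern.** Behaviours picked because they are currently the worst will, if they fluctuate, tend to look better later whether or not anything useful was done. A change in the home over 3 months, or familiarity with recording, could move the clips in the same way. A comparison of baseline with post-intervention clips cannot separate these from the effect of an intervention. Aim 1 is protected because randomized groups are compared. Aim 2, as written, has no such protection.

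At stake is the typology. Interventions could enter it as effective partly or wholly because they were recommended for behaviours that would have eased anyway. The exploratory label limits the strength of the claim but does not take the bias out of it.

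**Working it through.** **Plan's own figure.** Aim 2 has no stated power or precision. The nearest figure is in D2, for Aim 1: difference 29 points, SD 35 in both groups, 35 dyads per group, Type 1 error 0.05 (two-sided assumed), power 93%. The standardized difference is 29/35 = 0.83. The normal approximation gives 93.4% and the noncentral t 92.7%, so the figure reproduces. It belongs to the between-group comparison and says nothing about a before-after one.

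**Illustration of the drop at zero effect.** Expected drop = (1 − r) × SD × z.

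- SD = 35, from D2. The documents do not say that this is a single-occasion SD; taking it so is an assumption.
- r is the correlation between baseline and follow-up. It is not given; 0.3 to 0.7 is assumed.
- z is the mean excess of the chosen behaviours at baseline, in SDs over the average of comparable behaviours. It is not given; 0.25 to 1 is assumed. The factor (1 − r) applies to this definition only, not to an excess over the dyad's own usual level.

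| z | r = 0.7 | r = 0.5 | r = 0.3 |
|---|---|---|---|
| 0.25 | 2.6 | 4.4 | 6.1 |
| 0.5 | 5.3 | 8.8 | 12.2 |
| 1.0 | 10.5 | 17.5 | 24.5 |

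For example, 0.7 × 35 × 1.0 = 24.5 and 0.3 × 35 × 0.25 = 2.6. The range is about 3 to 25 points.

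**What a control contrast does.** If both arms choose targets alike, the same expected drop occurs in each and cancels in the difference of mean changes. D5 describes target selection after the assignment step, so that likeness is an assumption and not something randomization alone guarantees.

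**What it costs in precision.** SD of change = 35 × √(2(1 − r)), which is 27.1 at r = 0.7 and 41.4 at r = 0.3. With one change per dyad:

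| Estimate | Formula for SE | SE, r = 0.7 to 0.3 |
|---|---|---|
| Before-after, 35 dyads | SD of change × √(1/35) | 4.6 to 7.0 |
| Difference in change, 35 v 35 | SD of change × √(2/35) | 6.5 to 9.9 |
| Intervention used by 10 dyads v 35 controls | SD of change × √(1/10 + 1/35) | 9.7 to 14.8 |
| Intervention used by 5 dyads v 35 controls | SD of change × √(1/5 + 1/35) | 13.0 to 19.8 |

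**What it does not do.** Let interventions i and j in one category have mean changes Δi and Δj, and let c be the control change for that category. Then (Δi − c) − (Δj − c) = Δi − Δj. The order of interventions within a category is unchanged, so subtraction corrects the level of apparent benefit but not the ranking.

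**The case against.** The strongest case against has four parts.

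*The mechanism may be weak.* Targets are chosen by caregiver judgement, not by an extreme coded value, and may be persistent problems and not transient peaks. Three recordings per activity at each time point dampen chance variation. Caregivers trigger the recordings throughout, so similar clip selection operates before and after. D4 notes that new symptoms arise as the disease progresses, so untreated improvement is not assured. All of this stands. It makes the size uncertain; it does not supply a comparator.

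*The control arm is not untreated.* Control caregivers receive standardized guidelines by weekly nurse call, and the FamTechCare nurse's feedback draws on protocols referenced to the same appendix C. Subtraction may therefore remove real benefit common to both arms. This stands and must be stated with the result.

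*The aim is exploratory, descriptive and without a stated test.* True, and it keeps the matter modest. But the plan still undertakes to determine which interventions are effective.

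*Control clips may already be intended for use.* A reader might infer that Aim 2 excludes them. The documents do not support that: coding blind to group suggests they are in the coded set. What is missing is any statement that they will be compared.

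**Conclusion.** The point holds as a modest, inexpensive improvement. Following the plan as written, time trends and regression to the mean can be counted as intervention effect, because targets are selected as most problematic and no control contrast is stated.

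The 3 to 25 point range is illustrative and rests wholly on the assumed r and z and on reading 35 as a single-occasion SD. Three stronger readings are tempting and are not supported:

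- That regression would account for a particular share of the planned 29-point effect. Neither r nor z is documented, and the 29 and 35 are planning inputs for Aim 1.
- That subtracting the control change would yield a valid ranking of interventions. It leaves the order within a category as it was. It also leaves untouched the non-random choice and use of interventions, and the optimism of naming the best of many.
- That the trial's main comparison is compromised. Aim 1 compares randomized groups and is not affected.

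**What to change.** Add to D7b and D9b, and to the Aim 2 row of Table 1:

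1. For each behaviour category, using the clips coded at baseline, 1 and 3 months, report the FamTechCare change, the control change and their difference with an interval. Compare clips of similar baseline level where numbers allow.
2. Do not call an intervention effective on before-after change alone.
3. State that the contrast is with standardized phone guidelines and not with no treatment, and that it does not correct for how interventions were chosen or for selecting the best of many.
4. Label any ranking of single interventions hypothesis-generating.

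The extra clips that caregivers record after using an intervention (D5) need not have a control clip at the same interval. Report those descriptively and keep them out of the contrast.

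The cost is a little more analysis of data already coded, and wider intervals: the SE is about 1.41 (√2) times larger with equal groups, and larger still for rarely used interventions. No new data collection is needed.

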Cost Analyses. We anticipate that some or all intervention costs will be offset by savings for caregiver travel to frequent appointments and for professionals such as reduced health care provider time. We posit that these savings represent only part of the benefits, as reduced caregiver stress may improve caregiver health and reduce health care costs, improve quality of life, and reduce NH admissions. We will not measure these long term outcomes in this study, but we plan to build on this study's cost outcomes in future research. In this study, we will focus on accurately costing the intervention and on computing a simple cost-effectiveness ratio: the added cost for FamTechCare divided by the reduction in objective PWD disruptive behaviors and caregiver burden and desire for NH placement. We will use Cost-effectiveness Analysis (CEA) and Data Envelopment Analysis (DEA) to analyze this type of cost efficiency. CEA allows investigation of the cost of a single outcome; with DEA we investigate efficiency using multiple cost variables and outcomes (Hollingsworth, 2008).

Process-Based Costing of the Intervention. Following Lee et al.(2003), data will be collected to determine costs of the FamTechCare intervention. Specifically, we will identify resources used by caregivers and professionals in the intervention. Primary resource use will include costs for HMU equipment and professional

time spent in home visits, review of video data and care-planning, and providing specific feedback and caregiver instruction for managing behaviors. Other resources measured will include mileage, materials, equipment, phone, internet, and video conferencing. We will tabulate all resources used and calculate the cost of the FamTechCare intervention. We will separately report resource use and resource costs per HMU unit.

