Cost Effectiveness Analysis We will focus on collecting accurate cost data for delivering FamTechCare, analyzing the effects of the intervention on costs, and calculating a simple cost-effectiveness ratio. We will use DEA to analyze the net effect of the intervention on costs (Hollingsworth, 2008). This approach tests the hypothesis that the cost of FamTechCare will be offset by reductions in PWD disruptive behavior and caregiver burden. We will calculate a simple cost-effectiveness ratio: the incremental cost of FamTechCare divided by reductions in caregiver desire for NH placement, using the 6-item Desire to Institutionalize Scale (Morycz, 1985) with reported reliability of 0.69 (McCaskill et al., 2010).

D8. Data Management. De-identified descriptive data will be labeled with each participant's unique identifier code and promptly transferred to data files in the REDCap platform. REDCap is managed by the Institute for Clinical and Translational Science, the University of Iowa's CTSA. In REDCap, primary data and data backups are secured in two separate data centers. Operating system security includes secure logins, remote system logging and configuration, and change management. Data encryption occurs both in flight and at rest and copies of data are replicated to the remote data center every 15 minutes to facilitate data recovery. Data will be entered in separate electronic spreadsheets using only identifier codes to assure confidentiality and anonymity (see Human Subjects). Only the research team will have access to the key for participant identification codes.

D9. Data Analyses.

Randomization. [name] will develop the randomization scheme using a 1:1 allocation ratio. For each site, random numbers will be generated to determine a sequence of dyad assignment to either control or treatment. To ensure equal numbers in each group, a blocking strategy will be used with blocks of 4 dyads.

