Cost Effectiveness Analysis (CEA) focuses on cost per unit change in PWD disruptive behavior (Δ PDB), comparing change in the proportion of disruptive behaviors between groups post-intervention. The additional costs for FamTechCare will be termed Δ C. For our CEA we calculate a 95% confidence interval for the ratio Δ C/ Δ PDB, defined as the change in cost per unit change in disruptive behaviors. Δ PDB will be modeled using the linear mixed model. At the end of the analysis we will generate a 95% confidence interval for a ratio, which can be complicated due to non-normality of the distribution of the parameter estimate. However, we will use a bootstrap procedure (Efron & Tibshirani, 1993) to alleviate this challenge. We will repeat this CEA using caregiver burden as the change unit. Our economist co-investigator has published on CEA (Lee, 2008).

Data Envelopment Analysis (DEA) is an ideal approach for assessing efficiency in this study. DEA allows consideration of multiple non-monetary outputs (Cooper et al., 2004; Hollingsworth et al., 1999; Seiford & Thrall, 1990) and uses linear programming to generate a coefficient of efficiency that compares cost factors to outcomes (Seiford & Ahn, 1993), with a large coefficient identifying efficiency. DEA compares cases with similar resources rather than the average or an artificial "ideal" (Charnes et al., 1994). DEA is a form of multi-attribute benchmarking used extensively in hospitals and NHs (Athanassopoulos et al., 1999; Chattopadhyay & Ray, 1996). Our health economist expert will fit a DEA model to investigate the overall efficiency in intervention compared to control in reducing caregiver desire for NH placement (Cooper, et al., 2004; Lee et al., 2009).

D10. Timeline. The initial 4 months of this 4-year study will be used to hire and train research team members in study protocols, to negotiate data protection agreements, and to purchase and configure equipment. The intervention and data collection will be completed in waves (8 participants every 3 to 4 months) during months 4 to 44. Analyses and coding will begin in the second half of year 01 and will continue through Year 04. Data analysis, dissemination and reporting will be completed in the final 6 months.

Research Study Activity	Year 1/Quarter				Year 2/Quarter				Year 3/Quarter				Year 4/Quarter			
	1	2	3	4	1	2	3	4	1	2	3	4	1	2	3	4

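### DEA cannot test whether FamTechCare's cost is offset, and the plan names three different sets of DEA outputs

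*Combined protocol and SAP*

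**What the plan says.** **The claim.** D7c, Cost Effectiveness Analysis, states "We will use DEA to analyze the net effect of the intervention on costs" and then "This approach tests the hypothesis that the cost of FamTechCare will be offset by reductions in PWD disruptive behavior and caregiver burden".

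**The method.** D9c, Data Envelopment Analysis, says that "DEA allows consideration of multiple non-monetary outputs" and that the method "uses linear programming to generate a coefficient of efficiency that compares cost factors to outcomes". A large coefficient is read as efficient. No null value, test or interval is given for it. The application named there is to "fit a DEA model to investigate the overall efficiency in intervention compared to control in reducing caregiver desire for NH placement".

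**The expected source of savings.** D7c, Cost Analyses, says: "We anticipate that some or all intervention costs will be offset by savings for caregiver travel to frequent appointments and for professionals". It then mentions possible later gains in caregiver health, health care costs, quality of life and nursing-home admissions, and adds: "We will not measure these long term outcomes in this study".

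**The cost data.** D7c, Process-Based Costing, covers resources consumed in the intervention: equipment, professional time, mileage, materials, phone, internet and video conferencing. Table 1 gives study records as the cost source.

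**The concern.** A cost is offset when savings, or benefits valued in money, equal or exceed it. Disruptive behaviour is coded as a share of recorded time and burden is a questionnaire score. Neither can be subtracted from a cost unless a price is put on it. A DEA score ranks units against one another on inputs and outputs; it does not say whether money was saved. D7c therefore attaches a hypothesis to a method that cannot confirm or refute it.

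Two things are at stake. Aim 3 would have a stated hypothesis with no analysis able to address it, and a good efficiency score could be mistaken for evidence that the programme pays for itself. Also, because the outputs differ between sections, it is unclear which DEA model is the planned one.

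**Working it through.** The plan states no figure for the offset hypothesis, so there is none to reproduce. The check has four parts.

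**1. Units.** Behaviour is a proportion of time and burden a score from 0 to 44 (both D7a). An offset statement needs a net amount:

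net = (value per unit × units of improvement) − added cost

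The plan gives no value per unit. To show how much depends on it, take the 29-point reduction assumed in D2 and some added costs per dyad (my assumptions; the plan has none). The break-even value per percentage point is added cost ÷ 29:

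- 500 ÷ 29 ≈ 17
- 1,000 ÷ 29 ≈ 34
- 2,000 ÷ 29 ≈ 69
- 5,000 ÷ 29 ≈ 172

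Without a stated value, the same trial result can be called offset or not offset.

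**2. What a DEA score responds to.** In the input-oriented form, the score for dyad *o* is the smallest θ such that Σλⱼxⱼ ≤ θxₒ and Σλⱼyⱼ ≥ yₒ, with all λⱼ ≥ 0. Here *x* is cost and *y* the outputs. If every cost is multiplied by *k*, *k* cancels from the first constraint and θ does not change. The net amount above does change.

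One simulated data set shows this. All values are assumptions: 35 dyads per group; cost mean 2,000 (FamTechCare) and 600 (control); two outputs, reductions in behaviour and in burden; constant returns to scale. The simulated difference in behaviour reduction was 18.475 points. At an assumed value of 100 per point it is worth about 1,847.5.

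| All costs × | Added cost per dyad | Net at 100 per point | Mean DEA score, FamTechCare / control |
|---|---|---|---|
| 0.1 | 143 | 1,847.5 − 143 ≈ +1,704 | 0.30 / 0.53 |
| 1 | 1,430 | 1,847.5 − 1,430 ≈ +418 | 0.30 / 0.53 |
| 10 | 14,299 | 1,847.5 − 14,299 ≈ −12,452 | 0.30 / 0.53 |

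The largest change in any dyad's score was about 1e-16, which is rounding error. The same scores go with a net gain and with a large net loss.

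**3. Cost data.** The resources listed in D7c are those the intervention uses. Mileage and professional time appear in that role. No item records avoided appointments, avoided travel or health-service use in either arm.

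**4. DEA outputs by section.**

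| Place | Behaviour | Burden | Desire for placement |
|---|---|---|---|
| Section B, Aim 3 paragraph | yes | yes | yes |
| D7c, Cost Analyses | yes | yes | yes |
| D7c, Cost Effectiveness Analysis (DEA sentences) | yes | yes | no |
| D9c, Data Envelopment Analysis | no | no | yes |

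The two outcomes in the D7c hypothesis are the two that the D9c model does not name.

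**The case against.** The strongest reply is that the offset sentence is loose drafting. The paragraph is headed Cost Effectiveness Analysis, and offset may mean only worth the cost. On that reading, D9c already offers something useful: a bootstrap 95% interval for added cost per unit change in disruptive behaviour, repeated for burden. D9c also already describes DEA as a comparison of efficiency between arms. Part of this stands, since the ratios are informative about value for money. But a ratio becomes a test only against a value threshold, and none is given. D7c also assigns the hypothesis to DEA and speaks of a net effect on costs. The simulation bears on the monetary reading only.

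Three stronger inferences are tempting, and the documents do not support them:

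- *That the plan declares the offsetting savings unmeasured.* The sentence "We will not measure these long term outcomes in this study" refers to the long-term outcomes named just before it. It does not exclude travel or provider-time savings. The supportable statement is that no measure of those savings is listed.
- *That the DEA output is left entirely open until the data are seen.* Section B and D7c (Cost Analyses) name all three outcomes in advance for DEA, and Table 1 lists them under Aim 3. What remains is an inconsistency within a declared set of three.
- *That an efficiency score will be reported as proof of offset.* No section says so. It is a risk that the wording invites.

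**Conclusion.** The point holds in limited form. As written, the D7c hypothesis cannot be tested by DEA: the method gives a relative score, its outputs are not in money, no value or threshold is supplied, and no avoided-cost measure is listed. Under the looser reading of offset, the planned ratios inform the question but do not test it. Separately, the DEA outputs are inconsistent across sections and need to be reconciled.

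There is no numerical error to size. The conclusion rests on D9c's own description of DEA and on the cancellation shown above. The cost figures are assumptions and serve only as illustration. Severity is low: the point affects what Aim 3 may conclude and which outcomes enter the DEA. The randomised comparisons in Aim 1, the power calculation and the planned cost-effectiveness intervals are untouched.

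**What to change.** In D7c, Cost Effectiveness Analysis, replace the two DEA sentences with:

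> DEA will compare the relative efficiency of FamTechCare and control, using the cost variables as inputs and reductions in disruptive behaviour, caregiver burden and desire for NH placement as outputs; no claim that costs are offset will be made from DEA.

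In D9c, where the model is now described only as "in reducing caregiver desire for NH placement", name the same three outputs. Cost questions then rest on the cost-effectiveness ratios, with the bootstrap 95% intervals already planned for behaviour and burden.

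The required change is to wording, and its price is a narrower economic claim. It keeps the several cost inputs that D7c foresees. Comparing arms does need control-arm costs, which D7c does not clearly describe; the existing D9c comparison already depends on them, so the fix adds no new requirement.

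Two additions are optional. One is a bootstrap interval for the difference in DEA scores. This is extra analysis and would need rules for dyads that worsen and for resampling scores that share an estimated frontier. The other applies only if an offset claim is wanted: collect health-service, travel and provider-time costs in both arms and estimate the difference in total cost with a bootstrap interval, or report net monetary benefit over a range of stated values.
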